## 5.2 Enrollment and Retention of Trial Population

### 5.2.1 Recruitment Procedures

Before the start of the trial, the Investigator and / or study staff may contact the parent / guardian of an appropriate pool of potential subjects and invite them to participate in the study. The site will ensure that any advertisements used to recruit subjects (e.g., letters, pamphlets, and posters) (if applicable, according to country regulation and practice) are submitted to Sanofi Pasteur for review prior to submission to the IEC/ IRB for approval.

In addition, a parent who brings a child to the trial site for a routine visit will be invited to enroll the subject in the trial, if eligible. Subjects may also be recruited from the general population.

### 5.2.2 Informed Consent Procedures

Informed consent is the process by which a subject's parent(s) / guardian voluntarily confirms his or her willingness to allow the child to participate in a particular trial. Informed consent must be

obtained before any study procedures are performed. The process is documented by means of a written, signed, and dated ICF.

In accordance with GCP, prior to signing and dating the consent form, the subject's parent / guardian must be informed by appropriate study personnel about all aspects of the trial that are relevant to making the decision to participate, and must have sufficient time and opportunity to ask any questions.

**For subjects enrolled in Mexico, South Korea, and Thailand:** If the subject's parent / guardian is not able to read and sign the ICF, then it must be signed and dated by an impartial witness(es) who is independent of the Investigator, according to local regulations. A witness who signs and dates the consent form is certifying that the information in this form and any other written information had been accurately explained to and understood by the subject or his / her representative. This does not apply to subjects enrolled in the Russian Federation.

The actual ICF used at each center may differ, depending on local regulations and IEC / IRB requirements. However, all versions must contain the standard information found in the sample ICF provided by the Sponsor. Any change to the content of the ICF must be approved by the Sponsor and the IEC / IRB and the appropriate regulatory agencies according to local regulations prior to the form being used.

If new information becomes available that may be relevant to the subject's parent / guardian's willingness to continue participation in the trial, this will be communicated to him / her in a timely manner. Such information will be provided via a revised ICF or an addendum to the original ICF.

ICFs will be provided in duplicate (as originals), or a photocopy of the signed consent will be made, as per local regulations and practice. The original will be kept by the Investigator, and the copy, or the other original (as applicable) will be kept by the subject's parent / guardian.

Documentation of the consent process should be recorded in the source documents.

#### ***In the Russian Federation***

In the Russian Federation, as per local regulations, only the subject's parent(s) are entitled to sign an ICF. A child under the responsibility of a guardian will not be included in the study.

The signature of only one of the parents will be required on the ICF.

#### **5.2.3 Screening Criteria**

For South Korea, Mexico, and Thailand, there are no screening criteria other than the inclusion and exclusion criteria.

For the Russian Federation, as per Guideline for the conduct of clinical trials of the Russian Federation Health Authorities and in accordance with local practices, in addition to being tested for study vaccine immunogenicity assessment, the blood of subjects enrolled at sites in the Russian Federation will be tested for complete blood count (CBC) and blood chemistry. These subjects will also provide a urine sample for urinalysis. According to recommendations of Russian Health Authorities, the subjects will be examined by a neurologist.

The examinations by a neurologist and additional biological analyses have been implemented for subjects enrolled at sites in the Russian Federation per the request of the Russian Federation Health Authorities only and not to address any concern of the Sponsor regarding safety issues.

#### 5.2.4 Inclusion Criteria

An individual must fulfill *all* of the following criteria in order to be eligible for trial enrollment:

- 1) **For South Korea:** Korean males and females aged 12 to 23 months on the day of the first study visita  
**For Mexico:** Males and females aged 12 to 23 months on the day of the first study visit  
**For the Russian Federation:** Males and females aged 12 to 14 months or 16 to 23 months on the day of the first study visit (eligible for enrollment to Group 8) or 15 to 23 months on the day of the first study visit (eligible for enrollment to Group 7 or 9).b  
**For Thailand:** Thai males and females aged 12 to 23 months on the day of the first study visit.a
- 2) Subject had received all recommended standard of care vaccinations according to his/her age as per local regulations.c  
**For the Russian Federation only**, subjects aged 15 to 23 months on the day of the first study visit (eligible for enrollment to Group 7 or 9) must not have received the third PCV13 vaccination corresponding to his or her age as per the country's NIP. The 2nd dose of PCV13 must have been administered at least 4 weeks before the 3rd dose of PCV13 is administered in the study.  
**For South Korea**, subjects must not have received the MMR or V vaccination corresponding to his or her age at inclusion.  
**For Mexico**, subjects must not have received the DTaP-IPV-HB-Hib vaccination corresponding to his or her age at inclusion.  
**For Thailand**, subjects must not have received the MMR or V vaccination corresponding to his or her age at inclusion.

---

a “12 to 23 months” means from the 1st day of the 12th month after birth to the day before the 24th month after birth

b “12 to 14 months” means from the 1st day of the 12th month after birth to the day before the 15th month after birth; “15 to 23 months” means from the 1st day of the 15th month after birth to the day before the 24th month after birth; “16 to 23 months” means the 1st day of the 16th month after birth to the day before the 24th month after birth.

c Subjects must have received the total number of doses expected for each vaccine recommended for his/her age in the respective NIPs, but inclusion of subjects with variations in the vaccine administration timeframes is considered acceptable if the total number of doses for the corresponding vaccines have been completed (e.g., in Mexico, 3 infant doses of the pentavalent vaccine must have been administered but the 4th dose due in the 2nd year of life should not have been administered for subjects to be included in the trial). **For the Russian Federation only**, subjects that have not received a seasonal flu vaccination from 6 months of age according to the Russian NIP are still eligible to participate in this study. **For Thailand only**, subjects who may have received a vaccine ahead of the schedule can still be included in the study provided the first doses of MMR and V vaccines have not been administered prior to inclusion.

- 3) Informed consent form has been signed and dated by the parent(s) or guardian if allowed by local regulations (and by independent witnesses if required by local regulations)a
- 4) Subject and parent/guardian are able to attend all scheduled visits and to comply with all trial procedures

### 5.2.5 Exclusion Criteria

An individual fulfilling *any* of the following criteria is to be excluded from trial enrollment:

- 1) Participation in the 4 weeks preceding the first trial vaccination or planned participation during the present trial period in another clinical trial investigating a vaccine, drug, medical device, or medical procedure
- 2) Receipt of any vaccine in the 4 weeks (28 days) preceding the first trial vaccination or planned receipt of any vaccine prior to Visit 2 except for influenza vaccination, which may be received at least 2 weeks before or after the study investigational vaccines. This exception includes monovalent pandemic influenza vaccines and multivalent influenza vaccines.
- 3) Previous vaccination against meningococcal disease with either the trial vaccine or another vaccine (i.e., mono- or polyvalent, polysaccharide, or conjugate meningococcal vaccine containing serogroups A, C, Y, or W; or meningococcal B vaccine)
- 4) **For subjects enrolled at sites in the Russian Federation:** previous vaccination with the third dose of PCV13 in subjects 15 to 23 months of age (eligible for Group 7 or 9)
- 5) **For subjects enrolled at sites in Mexico:** known history of seizures, or uncontrolled neurologic disorder (including epilepsy); or encephalopathy of unknown etiology occurring within 7 days following previous vaccination with pertussis containing vaccine; previous vaccination with DTaP-IPV-HB-Hib or DTaP-containing vaccine at 12 to 23 months of age.
- 6) **For subjects enrolled at sites in South Korea and Thailand:** known history of seizures, cerebral injury, or encephalopathy; previous vaccination with MMR or V at or before 12 to 23 months of age.
- 7) Receipt of immune globulins, blood or blood-derived products in the past 3 months
- 8) Known or suspected congenital or acquired immunodeficiency; or receipt of immunosuppressive therapy, such as anti-cancer chemotherapy or radiation therapy, within the preceding 6 months; or long-term systemic corticosteroid therapy (prednisone or equivalent for more than 2 consecutive weeks within the past 3 months)
- 9) History of meningococcal infection, confirmed either clinically, serologically, or microbiologically
- 10) At high risk for meningococcal infection during the trial, according to the Investigator's judgment (specifically, but not limited to, subjects with persistent complement deficiency,

a **In the Russian Federation**, as per local regulations, only the subject's parent(s) are entitled to sign an ICF. A child under the responsibilities of a guardian will not be included in the study.

with anatomic or functional asplenia, or subjects traveling to countries with high endemic or epidemic disease)

- 11) Known systemic hypersensitivity to any of the vaccine components, or history of a life-threatening reaction to the vaccine(s) used in the trial or to a vaccine containing any of the same substancesa
- 12) Verbal report of thrombocytopenia, as reported by the parent/guardian, contraindicating intramuscular vaccination by the Investigator's judgment
- 13) Known bleeding disorder, or receipt of anticoagulants in the 3 weeks preceding inclusion, contraindicating intramuscular vaccination by the Investigator's judgment
- 14) Personal history of Guillain-Barré syndrome (GBS)
- 15) Personal history of an Arthus-like reaction after vaccination with a tetanus toxoid-containing vaccine
- 16) Chronic illness that, in the opinion of the Investigator, is at a stage where it might interfere with trial conduct or completionb
- 17) **For subjects enrolled at sites in South Korea, Mexico, and Thailand:** Moderate or severe acute illness/infection (according to Investigator's judgment) on the day of vaccination or febrile illness (temperature  $\geq 38.0^{\circ}\text{C}$ ). A prospective subject should not be included in the study until the condition has resolved or the febrile event has subsided.
- 18) **For subjects enrolled at sites in the Russian Federation:** Acute disease of any severity on the day of vaccination or febrile illness (axillary temperature  $\geq 37.0^{\circ}\text{C}$ ). A prospective subject should not be included in the study until the condition has resolved or the febrile event has subsided.
- 19) Receipt of oral or injectable antibiotic therapy within 72 hours prior to the first blood draw
- 20) Identified as a natural or adopted child of the Investigator or employee with direct involvement in the proposed study

## 5.2.6 Medical History

Prior to enrollment, subjects will be assessed for pre-existing conditions and illnesses, both past and ongoing. Any such conditions will be documented in the source document. Significant medical history (reported as diagnosis) including conditions for which the subject is or has been followed by a physician or conditions that could resume during the course of the study or lead to an SAE or to a repetitive outpatient care will be collected in the CRF. The significant medical history section of the CRF contains a core list of body systems and disorders that could be used to

a The components of the MenACYW conjugate vaccine are listed in [Section 6.1.1.1](#) and in the Investigator's Brochure. The components of MMR, V, DTaP-IPV-HB-Hib, and PCV13 are listed in [Section 6.1.2.1](#), [Section 6.1.3.1](#), [Section 6.1.4.1](#), and [Section 6.1.5.1](#), respectively.

b Chronic illness may include, but is not limited to, cardiac disorders, renal disorders, auto-immune disorders, diabetes, psychomotor diseases, and known congenital or genetic diseases.

prompt comprehensive reporting, as well as space for the reporting of specific conditions and illnesses.

For each condition, the data collected will be limited to:

- Diagnosis (this is preferable to reporting signs and symptoms)
- Presence or absence of the condition at enrollment

The reporting of signs and symptoms is strongly discouraged.

Dates, medications, and body systems are not to be recorded, and the information collected will not be coded. Its purpose is to assist in the later interpretation of safety data collected during the trial.

#### ***For the Russian Federation Only***

Any clinically significant abnormal results of the Visit 0 CBC, blood chemistry, urinalysis, or neurological examination, according to Investigator judgment will be reported as medical history. All laboratory tests will be sampled and analyzed locally. Results of the lab tests will be assessed by the Investigator. The Investigator should choose to not include the subject in the study if any of these laboratory tests have the potential to impact the health of the subject after vaccination. The laboratory values for CBC, blood chemistry, urinalysis, and the results of neurological examinations will only be collected in the CRF if they are clinically significant. Visit 0 laboratory tests are to be considered clinically significant in the following circumstances:

- Symptomatic
- Requiring corrective treatment or additional consultation by relevant specialist
- Leading to study vaccine discontinuation or postponing vaccination
- Meet SAE criteria

#### **5.2.7 Contraindications for Subsequent Vaccinations**

Not applicable since only one dose of the vaccine(s) will be administered on D0 in this trial.

#### **5.2.8 Temporary Contraindications for Visit 2 Blood Draw**

Should a subject receive oral or injectable antibiotic therapy within 3 days prior to the second blood draw, the Investigator will postpone that blood draw until it has been 3 days since the subject last received oral or injectable antibiotic therapy. Postponement must still be within the timeframe for blood draw indicated in the [Table of Study Procedures](#). If postponement would result in the sample collection falling outside of this timeframe, the blood sample should be collected without postponement and it should be documented appropriately that the sample was taken less than 3 days after stopping antibiotic treatment.

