## 6.7 Concomitant Medications and Other Therapies

At the time of enrollment, ongoing medications including other therapies e.g., blood products, should be recorded in the source document as well as new medications prescribed for new medical conditions / AEs during trial participation.

Documentation in the CRF of concomitant medication will be limited to specific categories of medication of interest beginning on the day of vaccination. This may include medications of interest that were started prior to the day of vaccination.

Reportable medications will be collected in the CRF from the day of vaccination to the end of the solicited and unsolicited follow-up period (e.g., 30 day safety follow-up) as they may impact the response to the vaccination and impact the consistency of the information collected on concomitant medications at any vaccination.

The “reportable” medications are distributed according to 3 categories. These are:

- Category 1 antipyretics, analgesics, non-steroidal anti-inflammatory drugs (NSAIDs), corticosteroids, and other immune modulators.

*Note: inhaled and topical steroids should not be captured.*

- Category 2: Reportable medications used to define the Per-Protocol Analysis Set (PPAS). For example:
  - Influenza and other non-study vaccines: Influenza vaccine in the 2 weeks preceding the trial vaccination up to the subject’s termination from the trial and any other vaccines (other than the study vaccine) in the 4 weeks preceding the trial vaccination up to the subject’s termination from the trial
  - Immune globulins, blood or blood-derived products: used in the 3 months preceding the first blood draw and up to the last blood draw
  - Immunosuppressive therapy such as anti-cancer chemotherapy or radiation therapy: used in the 6 months preceding the trial vaccination and the 4 weeks following the trial vaccination
- Category 3: Oral or injectable antibiotics, which may interfere with bioassays used for antibody testing when taken before a blood draw
  - The period of collection should be within 3 days before the first blood draw and up to the last scheduled blood draw.

*Note: Inhaled and topical antibiotics (drops, creams or ointments) should not be captured.*

The information reported in the CRF for each reported medication will be limited to:

- Trade name / International non-proprietary name
- Given as treatment or as prophylaxis
- Medication category
- Start and stop dates

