## 9 Endpoints and Assessment Methods

### 9.1 Primary Endpoints and Assessment Methods

#### 9.1.1 Immunogenicity

##### 9.1.1.1 Immunogenicity Endpoints

The primary endpoints for the evaluation of immunogenicity are:

Antibody (Ab) titers against meningococcal serogroups A, C, Y, and W measured by serum bactericidal assay using human complement (hSBA) for Groups 1, 2, 4, 5, 7, 8, 10, and 11 at Visit 0 (for subjects in the Russian Federation) or Visit 1 (for subjects in Mexico, South Korea, and Thailand) (before vaccination[s]) and 30 days (+14 days) after vaccination(s) (all subjects).

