## 9.3 Observational Endpoints and Assessment Methods

### 9.3.1 Immunogenicity

#### 9.3.1.1 Immunogenicity Endpoints

Ab titers against meningococcal serogroups A, C, Y, and W measured by rSBA before and 30 days (+14 days) after vaccination with MenACYW conjugate vaccine in 100 subjects from each of Groups 1, 4, and 7, and in 50 subjects from each of Groups 2, 5, and 8.

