### 12.2.3 Per-Protocol Analysis Set

The PPAS is a subset of the FAS. The subjects presenting with at least one of the following relevant protocol deviations will be excluded from the PPAS:

- Subject did not meet all protocol-specified inclusion criteria or met at least one of the protocol-specified exclusion criteria
- Subject did not receive vaccine
- Subject received a vaccine other than the one that he / she was randomized to receive
- Preparation and / or administration of vaccine was not done as per-protocol
- Subject did not provide the post-dose serology sample at Visit 2 in the proper time window or a post-dose serology sample was not drawn
- Subject received a protocol-prohibited therapy / medication / vaccine
- Subject's serology sample at Visit 2 did not produce a valid test result
- Subject had other protocol violation that affected the subject's immune response, as determined by the clinical team prior to locking the database

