### **5.2.2 Per-Protocol Analysis Set**

The PPAS is a subset of the FAS. The subjects presenting with at least one of the following relevant protocol deviations will be excluded from the PPAS:

- Subject did not meet all protocol-specified inclusion criteria or met at least one of the protocol-specified exclusion criteria
- Subject did not receive vaccine
- Subject received a vaccine other than the one that he / she was randomized to receive
- Preparation and / or administration of vaccine was not done as per-protocol
- Subject did not provide the post-dose serology sample at Visit 2 in the proper time window or a post-dose serology sample was not drawn
- Subject received a protocol-prohibited therapy / medication / vaccine
- Subject's serology sample at Visit 2 did not produce a valid test result
- Subject had other protocol violation that affected the subject's immune response, as determined by the clinical team prior to locking the database

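### Does the per-protocol set need a rule for Visit 2 sera drawn within 3 days of antibiotics?

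*Protocol*

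**What the plan says.** Protocol 5.2.8, repeated in the footnotes to the study-procedures tables of both documents, postpones the Visit 2 draw until 3 days after the last oral or injectable antibiotic dose. If that would leave the Day 30 to Day 44 window, "the blood sample should be collected without postponement and it should be documented appropriately that the sample was taken less than 3 days after" antibiotics were stopped.

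Protocol 6.7 sorts reportable medications into three classes. Antibiotics are in the third: "Category 3: Oral or injectable antibiotics, which may interfere with bioassays used for antibody testing when taken before a blood draw". The medications said to help define the per-protocol analysis set (PPAS) are in Category 2, whose examples are other vaccines, blood products and immunosuppressants.

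The PPAS exclusions are worded alike in protocol 12.2.3 and SAP 5.2.2. Two could bear on these sera. One applies when the child's "serology sample at Visit 2 did not produce a valid test result". The other is a catch-all for further violations that affected the immune response, "as determined by the clinical team prior to locking the database". Protocol 12.3.2 then analyses every subject in the relevant population who has valid data.

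For the baseline sample, exclusion criterion 19 in protocol 5.2.5 bars entry after "Receipt of oral or injectable antibiotic therapy within 72 hours prior to the first blood draw".

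**The concern.** The protocol warns of interference in one section, orders the sample to be taken in another, and says in neither what the analysis should do with the result. The two draws also seem to be treated unequally. Antibiotics shortly before the first draw breach an eligibility criterion, and so remove the child from the PPAS. The same exposure before Visit 2 has no stated consequence, although that sample supplies the post-vaccination titre for every primary hSBA summary.

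All immunogenicity analyses use the PPAS. A disturbed titre would therefore enter the GMTs, the percentages above the cutoffs and the seroresponse rates for hSBA (primary), and for rSBA (observational) in the groups tested.

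**Working it through.** The plan states no figure on this point, so there is nothing to reproduce. The check has three parts.

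**1. Which sera fall under the exception.** The last permitted day is Day 44 and the wait is 3 days. A last dose on Day 41 gives 41 + 3 = 44, inside the window, so the draw is postponed. A last dose on Day 42 gives 42 + 3 = 45, outside it, so the exception applies. Only children whose last dose falls on Day 42 or later, including courses still running, are concerned.

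**2. The eight PPAS exclusions against such a serum.**

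- Eligibility: criterion 19 covers the first draw only.
- No vaccine, wrong vaccine, faulty preparation or administration: not relevant.
- Time window: the draw is inside it.
- Prohibited medication: nothing prohibits antibiotics after vaccination.
- Invalid result: applies if the laboratory rejects the result. The text does not tie validity to antibiotics.
- Catch-all: a poor fit, because the draw follows 5.2.8 and the worry is the assay, not the immune response.

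A result that the laboratory accepts therefore stays in.

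**3. Size.** Children planned for hSBA (Groups 1, 2, 4, 5, 7, 8, 10 and 11): 100 + 50 + 200 + 100 + 200 + 100 + 100 + 50 = 900. The documents give no share of affected sera and no direction or size of error. I assume a share *f* of 0.1% to 1% (0.9 to 9 children) and an error *e* of 0.5 to 1.5 log10 in either direction.

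GMT factor = 10^(±*f* × *e*):

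- *f* = 0.001, *e* = 0.5: 10^0.0005 = 1.0012, about 0.1%
- *f* = 0.005, *e* = 1.0: 10^0.005 = 1.0116, or +1.2%; downward −1.1%
- *f* = 0.01, *e* = 1.5: 10^0.015 = 1.0351, or +3.5%; downward −3.4%

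In a group of 50, one child is already a share of 1/50 = 0.02:

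- *e* = 0.5: 10^0.01 = 1.023, or +2.3%; downward −2.3%
- *e* = 1.5: 10^0.03 = 1.072, or +7.2%; downward −6.7%

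For seroresponse I start from the lowest hSBA rate reported for serogroups A, Y and W in MET54 (protocol 1.2.2.4), 87/90 = 96.7%, with *f* = 0.01:

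- False highs can act only on non-responders: 0.01 × 3/90 = 0.03 points.
- False lows can act only on responders: 0.01 × 87/90 = 0.97 points.

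One misread child is 1/50 = 2 points in a group of 50, and 1/100 = 1 point in pooled Groups 2 and 11. For scale, 48/50 is 96.0% with a Clopper-Pearson interval of 86.3% to 99.5%. One responder fewer, 47/50, is 94.0% with 83.5% to 98.7%. The 2-point shift compares with an interval 99.5 − 86.3 = 13.2 points wide.

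A harsher assumption is a 5% share. In a group of 200 with 193 responders (96.5%; 92.9% to 98.6%), 10 sera all misread low give 183/200 = 91.5% (86.7% to 95.0%). If 5% of sera read four two-fold dilutions too high, the GMT factor is 2^(4 × 0.05) = 1.15.

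**The case for a change.** The best case for a written rule is that it would cost little and replace discretion. The trial is open-label, and the clinical team settles doubtful cases before lock. The exploratory full analysis set gives no check on this point: it contains the same sera and readmits children with other deviations. Sites must document these draws, yet no planned analysis uses the record. All of that stands, as does the point that one child matters more in the groups of 50.

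It does not carry the case for a change, for four reasons.

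- Section 6.7 speaks of bioassays without naming hSBA or rSBA. Including them is a fair inference, but the assay descriptions (protocol 9.1.1.2 and 9.3.1.2) are missing or redacted in the public copy. They may describe how antibiotic-containing serum is handled. Protocol 11.2 leaves validation of these data to laboratory procedures, and a rejected result leaves the PPAS under the invalid-result exclusion.
- The text can be read as having already chosen: take the sample, record the exposure, keep the result if valid. Preferring exclusion is then a different judgement, not the repair of an error.
- Criterion 19 is a weak comparison. Before vaccination, enrolment can wait. At the end of the Visit 2 window the alternative is to lose the only post-vaccination sample of a vaccinated child.
- Mandatory exclusion has its own price. It would put a rule about single assay results into a set defined by subject, so denominators would differ by assay, with no evidence on the direction or frequency of interference.

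**Conclusion.** No change is needed. No visible PPAS exclusion names these sera, but this is a missing detail that analysts can handle sensibly, and following the plan as written leaves the conclusions sound. No hypothesis is tested (protocol 12.1.1.1, SAP 5.1.1), so no success criterion can turn on a few sera.

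Under the assumed share of 0.1% to 1% and error of 0.5 to 1.5 log10, a GMT moves by about 0.1% to 3.5%. One affected child in a group of 50 moves it by about 2% to 7%, and a percentage by at most 2 points. A 5% share would be visible, but it would need one serum in twenty to come from children whose last antibiotic dose was on Day 42 or later. Nothing in the documents suggests that, and nothing in them excludes it.

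Protocol 6.7 already collects antibiotic start and stop dates up to the last scheduled draw. The affected sera can therefore be counted at the pre-lock data review (SAP 5.6), and the summaries can be repeated without them if the count is not negligible. The judgement rests on the exception being rare and on ordinary laboratory validation. The public text does not allow either to be verified.
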